#### c. Undesirable Effect

Any noxious and unintended response to an investigational drug at any dose or to any investigational component. An adverse reaction is serious if it meets a severity criterion.

#### d. Unexpected Serious Adverse Effect

An unexpected serious adverse reaction is an event that is not mentioned, or that differs in nature, intensity, or evolution from the product reference document (or RCPs).

#### e. New fact

A new fact can be: an unexpected frequency of an expected SAE, an SAE related to the trial procedure.

#### f. Intensity (or severity)

The intensity criterion should not be confused with the severity criterion, which is used as a guide to define reporting obligations.

The intensity of the events will be estimated according to the extract of the NCI CTC-AE classification version 4.0 (Appendix 7). The intensity of adverse events not listed in this classification will be assessed according to the following qualifiers:

- Mild (grade 1): does not affect the patient's usual daily activity
- Moderate (grade 2): disrupts the patient's usual daily activity
- Severe (grade 3): prevents the patient's usual daily activity
- Very severe (grade 4): requires resuscitative measures / life threatening
- Death (grade 5)

#### g. Causal relationship

- Related: an event is said to be related when a causal relationship between the event and the product under study can reasonably be suspected
- Unrelated: an event is said to be unrelated when a causal relationship between the event and the product under study cannot reasonably be suspected
- Doubtful: causality is said to be "doubtful" when there is doubt about the causal relationship between the event and the product under study (the relationship can then be neither formally excluded nor formally affirmed)

### 10.3 Reference documents for the study

The reference document for assessing the expected or unexpected nature of the SAEs will be, for regorafenib, the Summary of Product Characteristics for STIVARGA® 40 mg (Appendix 8).

The version of the PCRs used for the definition of expected/unexpected will be the latest available on the anniversary date of the start of the trial.

## 10.4 Events of particular interest, to be declared as a SAE

Within the framework of this protocol, we ask you to report on the SAE form, even if none of the classic severity criteria are met:

- Grade 3-4 liver function tests
- hepatic insufficiency

## 10.5 Events not to be considered serious

Disease progression should not be considered an SAE.

Events that are potentially related to progression but may also be secondary to treatment will continue to be reported (e.g. thromboembolic events, bleeding phenomena, perforations).

Due to the severity of the disease in this study, certain conditions defined as an SAE will be excluded from the SAE reporting procedure, namely:

- Hospitalization or surgery specifically related to the treatment of the disease
- Hospitalization performed to simplify study treatments or procedures.

## 10.6 Conduct

The investigator informs the sponsor of all Serious Adverse Events (expected and unexpected), whether or not attributable to the research, that occur during the study or within 30 days of the last treatment administration.

The investigator informs the sponsor of all Adverse Events of Special Interest (even "non-serious" ones) that occur during the study or within 30 days of the last treatment administration.

All Delayed Serious Adverse Events (occurring after this 30-day period) considered reasonably related to the protocol treatment(s) or research should be reported without time limitation.

The report is made by faxing the "notification of a serious adverse event" form (Appendix 9), documented as precisely as possible, dated and signed, within 24 working hours of their knowledge to the **FFCD's Randomization Management Analysis Center (CRGA) by fax to [name].**

The investigator is responsible for appropriate medical follow-up of patients until resolution or stabilization of the effect or until the patient's death. This may sometimes involve extending follow-up after the trial patient's protocol treatment has been discontinued.

It transmits the additional information to the sponsor using an SAE reporting form (checking the "Follow-up" box and incrementing the number, to specify that it is a follow-up report and not an initial report) within 24 hours of obtaining it. It also forwards the last follow-up to the resolution or stabilization of the SAE.

It responds to requests for additional information to document the initial observation.

The sponsor is responsible, upon receipt of the investigator's report of the serious adverse event, for issuing an opinion on the causal relationship between the serious adverse event and the study product(s).

If the serious adverse event is linked by the investigator and/or sponsor to one of the study products (i.e., it is a serious adverse event), the investigator and/or sponsor must establish the expected or unexpected nature of this event.

In the case of an unexpected serious adverse reaction, or if it is a new event, the sponsor prepares an initial report which will be sent to the ANSM, the CPP and the EMA (via EudraVigilance) within 7 days in the case of death or life-threatening situation, otherwise within 15 days.

If it is an expected serious adverse event, it will be collected for the semi-annual and annual safety reports.

## 11. STATISTICAL ANALYSIS

### 11.1 Judging criteria

#### 1) Primary endpoint

Tumor control rate is defined as the percentage of patients with complete tumor response, partial tumor response, or tumor stability on regorafenib therapy at 2 months after initiation of therapy as determined by the investigator (RECIST V1.1 criteria)

#### 2) Secondary criteria

The **secondary endpoints** are defined as follows:

- Overall treatment **tolerance** will be assessed by the rate of observed toxicities, graded according to NCI-CTC v4.

- **Overall survival is** defined as the time from the date of inclusion to the date of death from any cause. Patients lost to follow-up or alive at the time of analysis will be censored at the date of last report. A minimum follow-up of 1 year for the last included patient is required.

- **The tumor control rate** assessed in centralized review is defined as the percentage of patients with complete tumor response, partial tumor response, or tumor stability on regorafenib therapy 2 months after the start of therapy (RECIST criteria V1.1).

- **The objective response rate is** defined as the occurrence of at least one complete or partial response assessed from the best response (according to RECIST v1.1 criteria) during the treatment evaluations (Appendix 4). Patients who discontinue the study without response assessment will be considered non-responders.

- **Time to treatment failure is** defined as the time from the date of inclusion to the date of treatment discontinuation (regardless of cause) or death (regardless of cause). Living patients without treatment discontinuation will be censored at the date of last treatment administration.

- **Progression-free survival is** defined as the time from the date of inclusion to the date of first investigator-rated progression (clinical or radiological) or death (from any cause). Patients alive without progression will be censored at the date of last news. A minimum

follow-up of 1 year for the last included patient is required.

- **The regorafenib dose intensity** will be calculated during the first 2 cycles of treatment **and over the** entire treatment period. The theoretical dose intensity (TDI) (mg/cycle) is 3360 mg ((160mg/d x 21d ). The dose intensity (DI) actually received is equal to the total dose received divided by the total duration of treatment. The relative dose intensity (DIR) is equal to DI / DIT.

- **Time to deterioration in independence** is defined as the time from the date of inclusion to the date on which the IADL score (Appendix 2) has decreased by at least 1 point from the score calculated at inclusion. Patients alive or deceased without deterioration of autonomy will be censored at the date of last IADL assessment or the date of death.

- **Time to deterioration in quality of life** is defined as the time from the date of inclusion to the date of deterioration of the Spitzer QoL Index (9) (Appendix 3) by 2 points from the score at inclusion. Patients alive or deceased without deterioration will be censored at the date of last QoL assessment or the date of death.

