## EXAMINATION AND FOLLOW-UP SCHEDULE

	Before inclusion			During treatment (until progression)					After treatment
	J -21	J -14	J -7	C1 : D1, D7 and D14 C2 : D1, D7 and D14	D1 of each cycle (every 4 weeks)	D14 of each cycle	Every 8 weeks after the start of treatment	End of treatment visit	Every 8 weeks
Informed consent	X								
Clinical examination		X		X	X		X	X	X
Weight, height, BP		X		X	X		X	X	
ECOG		X			X		X	X	X
Geriatric questionnaires, quality of life		X			X		X		
Biological check-up 1 			X		X		X		
Biological check-up 2 						X		X	
Urine dipstick ± 24h proteinuria		X			X		X		
ECG		X			X 				
Thoracic and abdominal-pelvic CT	X						X		
ACE			X		X		X		
Cardiac ultrasound or myocardial scintigraphy ± cardiological opinion in case of cardiopathy 	X								
Assessment of treatment toxicity				X	X		X	X	

Biological check-up 1: CBC-PQ, natraemia, kalemia, calcemia, magnesemia, phosphoremia, uricemia, creatininemia, albuminemia, ASAT, ALAT, PAL, total and conjugated bilirubinemia, GGT, TP, TSH, lipase, INR for patients treated with AVK.

Biological check-up 2: CBC-Pq, natraemia, kalemia, creatinine, creatinine clearance, ASAT, ALAT, PAL, total and conjugated bilirubin, GGT INR for patients treated with AVK.

 For patients treated with an anti-coagulant, a coagulation test should be performed, if the values are outside the therapeutic range the dose of anticoagulant should be modified and a coagulation check should be done every week until stabilization.

 During treatment, an ECG will be done according to the investigator's choice.

 In case of heart disease, cardiac echography or myocardial scintigraphy, completed by a cardiologist's opinion if necessary, **dated less than 3 months before inclusion.**

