### 7.1 Duration of treatment

Causes of discontinuation are:

- progress
- occurrence of a second cancer
- Dose reduction of more than 2 times 40 mg
- interruption of treatment for more than 4 consecutive weeks
- patient refusal
- withdrawal of consent
- continuation of the study deleterious to the patient according to the investigator

Patients who discontinue study treatment will be managed according to local guidelines. The administration of any other anti-cancer treatment will be collected in the observation booklet at a follow-up visit.

Patients will be followed every 2 months after discontinuation of treatment, regardless of the reason for discontinuation, until death except for patients who have withdrawn their consent.

Patients who stopped treatment before progression will be followed to assess the date of first progression.

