## 8. PATIENT MONITORING

### 8.1 during treatment :

- Clinical examination: weight, height, BP, collection of toxicities and clinical tumor assessment

- Cycle 1 and 2: at D1, D7 and D14
- Cycles 3 and following: at D1 of each cycle
- At the end of treatment visit

The ECOG is completed on Day 1 of each cycle (cycle 1 and following) and at the end-of-treatment visit.

- Bioassay:

At each cycle: at D1 and D14; (for cycle 1, the biological test at D1 can be the inclusion test, if it is less than 14 days old).

The assessment at Day 1: CBC-platelets, natraemia, kalemia, calcemia, magnesemia, phosphoremia, uricemia, creatininemia, creatinine clearance, albuminemia, ASAT, ALAT, PAL, total and conjugated bilirubinemia, GGT, TP, TSH, lipase, INR for patients treated with AVK.

Assessment at D14: CBC/blood platelets, creatinine clearance, natraemia, kalemia, creatinine, ASAT, ALAT, PAL, total and conjugated bilirubin, GGT, INR for patients treated with AVK.

- At the end-of-treatment visit: CBC/blood platelet count, natraemia, kalemia, creatinine, creatinine clearance, AST, ALT, PAL, total and conjugated bilirubin, GGT

A coagulation test should be performed at D1 and D14 of each cycle, if patients are treated with anticoagulant. If the values are outside the therapeutic range, the dose of anticoagulant should be modified and a coagulation test should be performed every week until stabilization.

- Other follow-up:

During treatment, an ECG will be performed if deemed useful by the investigator.

Every 4 weeks, until progression, CEA measurement will be performed as well as quality of life and geriatric parameters assessment.

Every 8 weeks, until progression, a thoraco-abdomino-pelvic scan will be performed to evaluate the tumor response.

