## **8.2 After treatment :**

- If treatment is stopped for progression: the patient will be followed up approximately every 8 weeks to collect survival data and subsequent anti-cancer treatments.

- if the treatment is stopped for another reason: the patient will be followed every 8 weeks with a thoraco-abdomino-pelvic scanner, until progression. Then he will be followed approximately every 8 weeks to collect survival data and subsequent anti-cancer treatments.

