3.2 Conventions

Time since inclusion will be defined as the time elapsed since the day of inclusion, with the day of inclusion being considered as day 1.

Therefore, the durations will be calculated according to the following rule, e.g. for the time from death to inclusion: day of death - day of inclusion + 1.

The day before the day of inclusion (resp. the day before the day of treatment) will be considered as day -1 (day 0 does not exist).

The date of last news will be the date of the last examination performed or the last treatment or the last medical consultation/visit.

The following conversion rules will be used for the conversion of the number of days to months or years: 1 month = 30.4375 days; 1 year = 365.25 days.

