4.4.5 Progression-Free Survival

4.4.5.1 Definition

Elle est définie comme l'intervalle de temps entre la date d'inclusion et la date de 1^{ère} progression radiologique et/ou clinique selon l'investigateur ou la date de décès (quelle qu'en soit la cause). Les patients vivants et sans progression seront censurés à la date de dernières nouvelles. Un minimum d'un an pour le dernier patient inclus est nécessaire.

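### Censoring PFS at the date of last news can overstate the later PFS rates, including 1-year PFS, for living patients whose scans stop before progression

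*Protocol*

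**What the plan says.** Protocol 11.1 (secondary criteria) defines PFS from inclusion to first progression as judged by the investigator, on clinical or imaging grounds, or death from any cause. The censoring rule is: "Patients alive without progression will be censored at the date of last news". SAP 4.4.5.1 gives the same rule in French: "Les patients vivants et sans progression seront censurés à la date de dernières nouvelles". SAP 3.2 defines the date: "The date of last news will be the date of the last examination performed or the last treatment or the last medical consultation/visit". None of these contacts has to include a tumour assessment, and the treatment is not limited to regorafenib.

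The planned imaging is as follows.
- Protocol 8.1, on treatment: "Every 8 weeks, until progression, a thoraco-abdomino-pelvic scan will be performed to evaluate the tumor response".
- Protocol 8.2, after stopping for a reason other than progression: "the patient will be followed every 8 weeks with a thoraco-abdomino-pelvic scanner, until progression".
- Protocol 7.1: "Patients who stopped treatment before progression will be followed to assess the date of first progression".
- Examination and follow-up schedule, row "Thoracic and abdominal-pelvic CT": marked before inclusion and every 8 weeks during treatment, with no mark in the after-treatment column. Clinical examination and ECOG are marked there.

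PFS at 1 year is a named secondary objective (Protocol 2.2, SAP 1.1.2). SAP 4.4.5.2 asks for Kaplan-Meier rates at 6, 9, 12 and 18 months.

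**The concern.** A contact shows that the patient is alive, so last news is the right censoring date for overall survival. It does not show that the tumour has not progressed. A living patient who is no longer scanned, and for whom no clinical progression is recorded, is counted as progression-free up to the last contact.

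The plan handles its other timed endpoints differently. Time to loss of independence and time to deterioration in quality of life are censored at the last assessment of their own measure, or at death. PFS has no such link to tumour assessment.

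The later PFS rates are at stake, because few patients remain at risk there. One patient of 42 is 1/42 = 2.4 points.

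**Working it through.** **The plan's own figure.** The documents give no event count, rate or power for PFS. The only stated design is for the primary endpoint: 42 patients, success at 16 or more, 25% against 47%. It reproduces from the exact binomial: P(X ≥ 16 | 42, 0.25) = 0.0416 and P(X ≥ 16 | 42, 0.47) = 0.9057. PFS does not enter it.

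**Direction.** The Kaplan-Meier estimate is S(t) = Π(1 − d_j/n_j). Moving a living patient's censoring date from the last scan to a later contact leaves every d_j as it was and adds 1 to n_j at each event in between. For example, one event among 5 at risk gives 1 − 1/5 = 0.800, and among 6 it gives 1 − 1/6 = 0.833. No factor can fall, so the curve is unchanged or higher.

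**Size.** Inputs from the documents:
- scans every 8 weeks (56/30.4375 = 1.84 months)
- 2 patients per month, so 42/2 = 21 months of accrual
- at least 12 months of follow-up, so analysis at month 21 + 12 = 33

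Inputs that are **assumed**, because the documents are silent:
- exponential time to progression, median 2, 3 or 4 months
- exponential survival after progression, median 4 or 8 months
- 5%, 10%, 20% or 30% of patients have no scan after their first or second one
- no clinical progression is recorded for those patients

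Only patients not yet progressed at their last scan are affected: 2.0% to 18.9% of all patients across the scenarios. Those who are also alive at analysis, whose censoring date the rule governs, are 0.2% to 6.8%, or about 0.1 to 2.8 of 42.

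Each scenario was simulated with 200,000 patients under complete imaging, under last-news censoring, and under censoring of living patients at the last scan. Deaths stay events throughout. Each cell gives PFS at 6 / 12 months in percent.

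| Median to progression / after it (months); share stopping scans | Complete imaging | Last news | Last assessment | Last news minus last assessment (points) |
|---|---|---|---|---|
| 2 / 4; 5% | 14.6 / 2.1 | 15.5 / 2.7 | 15.4 / 2.5 | 0.1 / 0.2 |
| 3 / 4; 10% | 27.8 / 7.6 | 29.6 / 9.3 | 29.2 / 8.6 | 0.4 / 0.7 |
| 3 / 8; 20% | 27.8 / 7.7 | 32.1 / 13.0 | 30.6 / 10.3 | 1.5 / 2.7 |
| 4 / 8; 30% | 38.6 / 14.8 | 44.6 / 23.4 | 42.3 / 18.6 | 2.3 / 4.8 |

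The first and last rows are the extremes of the last column over all 24 scenarios. The median under last news equals that under complete imaging in every scenario, and under last assessment it shifts by at most 0.01 month.

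**What the change does not repair.** In the last row, last news exceeds complete imaging at 12 months by 23.4 − 14.8 = 8.6 points. The new rule removes 23.4 − 18.6 = 4.8 and leaves 18.6 − 14.8 = 3.8. That remainder comes from patients whose unseen progression is replaced by a later date of death.

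**The case against.** The strongest reply is that the protocol text does not plan for imaging to stop early. Sections 7.1, 8.1 and 8.2 require follow-up to progression, with 8-weekly scans even after treatment ends for another reason. For a patient scanned on schedule, last news falls at most about 8 weeks after the last scan. Clinical progression and death also count as events, and on-treatment visits include a clinical tumour assessment, so a visit is not empty of information. PFS is secondary and descriptive in a single-arm trial, with no test or threshold, and protocol and SAP agree on the rule. All of this stands, and it makes the effect conditional and modest. It does not supply a reason to use a contact date for a tumour endpoint, and the schedule table leaves room for follow-up visits without CT.

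A reader might infer more: that PFS is overstated as a matter of fact, by 2 to 8 points at 6 months. That follows if 47% at 2 months is read as exponential PFS. Then 6-month PFS is 0.47³ = 10.4% and week-8 PFS is 0.47^(1.84/2) = 49.9%. With a share f unassessed after week 8, (1 − f) × 10.4 + f × 49.9 gives 12.4%, 14.3% and 18.3% for f = 5%, 10% and 20%.

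The documents do not support that reading. The 47% is an expected tumour control rate, with patients who stop early counted as failures, not a PFS figure. The sum also needs every unscanned patient to stay alive and free of recorded clinical progression throughout, in a trial whose entry criterion is a life expectancy of only 3 months or more.

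**Conclusion.** The point holds as a conditional one. The rule can overstate the later PFS rates, including 1-year PFS, for living patients whose imaging stops before progression. Whether it does so in this trial depends on how many scans are missed, which the documents cannot tell us.

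Under the assumed ranges, changing the rule lowers 6-month PFS by about 0.1 to 2 points and 12-month PFS by about 0.2 to 5 points. These sizes lean high, because they assume that no clinical progression is recorded for unscanned patients and treat only scans as assessments. The median is in effect unmoved, and the primary decision rule (16 or more of 42) is untouched. This is an inexpensive improvement, not a flaw that threatens the trial's conclusion.

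**What to change.** - In SAP 4.4.5.1, censor living patients without progression at the last tumour assessment showing none. Count a scan or a documented clinical tumour assessment, and use day 1 if there is none.
- Keep last-news censoring as a sensitivity analysis, so that the effect of missed scans can be seen.
- Reconcile the schedule table with Protocol 8.2 on CT after treatment. As written they differ.

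The cost is a few sentences and one extra Kaplan-Meier run. SAP 1.6 allows changes until the database is frozen. The downside is slightly earlier censoring and a slightly less favourable late PFS rate. Unseen progressions later replaced by a death date remain uncorrected, and the report should say so.

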## **11.2 Exploratory evaluation of geriatric parameters**

It is recommended that each patient has had a geriatric consultation prior to inclusion.

An exploratory analysis is planned to look for geriatric prognostic factors for the primary endpoint. An analysis of the evolution of geriatric parameters during the follow-up will also be performed.

The "patient" self-questionnaire including the collection of activity of daily living and the "team" questionnaire including the quality of life (Spitzer QoL Index) will be completed at inclusion and at each evaluation (every 4 weeks).

The self-questionnaire will be completed by the patient. The "team" questionnaire will be completed by a clinical research associate, a nurse or the investigator depending on the organization of the service.

The 2 questionnaires include the assessment of geriatric parameters with the following domains: functional status, mobility, cognition, depression, energy, social context and quality of life; physical activity, nutrition, hearing and vision will only be completed at inclusion. A cut-off value is determined for each domain.

The questionnaires and self-questionnaires are presented in Appendices 2 and 3. These evaluation questionnaires have been used in onco-geriatrics, particularly as self-questionnaires (10-14).

